effects. In addition, preemptive testing allows genotyping samples from many patients to be batched and run in high volume, which substantially decreases the genotyping cost per patient. Thus, the most feasible/sustainable way to facilitate the clinical implementation of PGx in underserved patients will likely involve preemptive genotyping.

To our knowledge, there have been no studies reporting implementation data of preemptive PGx testing in medically underserved patients. Further, there are few data in the literature regarding the perceptions and attitudes of black and Latino patients toward preemptive PGx testing. This work is significant because it is expected to contribute valuable data toward both the feasibility of preemptive PGx testing in medically underserved patients, an area of PGx research where little information is available. We anticipate these data will inform future multi-site clinical trials of preemptive PGx implementation.

5. Specific Aims:

Motivated by the critical need to expand access of preemptive PGx testing to underserved populations, the overall objective for this application is to develop key feasibility data to equitably advance preemptive PGx testing within UF Health, and to generate important preliminary data to support future funding applications. The rationale for this project is that generating these feasibility data should facilitate equitable clinical implementation that may reduce medication treatment disparities, as well as inform future larger clinical studies. We plan to accomplish the overall objective of this application by pursuing three specific aims:

1. Assess the feasibility of preemptive PGx clinical implementation in primary care clinics predominantly serving medically underserved patients. We will provide clinical preemptive PGx testing for 100 patients from specific UF Health clinics serving mostly medically underserved patients, including clinics with a high rate of black and Latino patients. We will assess feasibility of this implementation effort by comparing patient-reported outcomes data abstracted from electronic health records before and 6 months after PGx testing.

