Patients may be approached for the study in various way including clinic intercepts, study flyers and clinic referrals. The electronic health record will be queried to identify potentially eligible participants using the inclusion/exclusion criteria. Providers (including but not limited to physicians, nurse practitioners, and pharmacists) who care for patients at UF Health will be notified when their patients qualify for the study and will be asked to discuss the study with their patients.

Patients can be recruited by study staff via two methods:

1. Clinic providers or staff ask patients if they are interested in participating and they acknowledge that they are interested.
2. Clinic provider or staff will provide patients an approved flyer and they contact study staff if interested.

If recruitment occurs during a clinic visit, patients meeting eligibility criteria will be approached by a research coordinator about study participation. Patients may also be contacted via phone after their clinic visit if in-person contact is not possible (for example, but not limited to, space limitations due to COVID-19 restrictions).

A research coordinator will review the consent document with the patient prior to enrollment. The consenting process can be in-person or remote via telephone or through electronic means. Prospective research participants will have the opportunity to ask questions before providing consent and will be provided with a signed copy of the consent form.

After providing written informed consent, a DNA sample will be collected from all patients by saliva (via mouthwash swish and expectorate collection) or buccal cell (via buccal brush/swab). If the genotyping fails with initial sample collection, the patients may be mailed a DNA collection kit for saliva or buccal cell sample collection for retesting.

Study design. After eligible participants provide written informed consent and are enrolled, a DNA sample will be obtained for PGx testing and questionnaires (as described below) will be administered at baseline, and then again at 3 months and 6 months after PGx results are entered into the EHR. Information will be abstracted from the EHR including PGx test results, medication changes, and healthcare provider encounters over the 6-month study duration (Table 1). A 1-month window will be permitted for each follow-up study interaction (\pm 15 days of exact due date).

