PGx testing will be completed using the GatorPGx panel, which is already available for clinical use in the CAP/CLIA certified UF Molecular Pathology Laboratory. Once results are entered into the EHR, Clinical Decision Support Best Practice Advisories already built into Epic will alert providers if a PGx interaction

might occur with a medication they prescribe. All clinical medication decisions will be made at the discretion of the healthcare provider.

Feasibility data collection:

The primary feasibility outcome will be change in patient treatment satisfaction between baseline and 6 months after PGx testing. This patient reported outcome will be measured via the Treatment Satisfaction Questionnaire for Medication (TSQM). The TSQM is a validated tool that assesses three medication-related domains (effectiveness, side effects, and convenience) to synthesize a global satisfaction score.^{5,6} Both global satisfaction and scores from individual domains will be analyzed.

Table 1. Proposed outcomes/measures to be tested

Outcome/Measure	Data source/Instrument	Ascertainment method	Baseline	3 mo.	6 mo.
Implementation Outcomes					
Treatment satisfaction	Treatment Satisfaction Questionnaire for Medication (TSQM)	Online or by phone	X	X	X
Medication adherence	Adherence Questionnaire	Online or by phone	X	X	X
Perceived value	Patient reported value	Online or by phone	X	X	X
Time discussing meds w/ healthcare provider	Patient reported estimate	Online or by phone	X	X	X
Effectiveness Outcomes					
Medication changes	EHR data	EHR data pull	X		X
Provider encounters	EHR data	EHR data pull	X		X
Socioeconomic Measures					
SEI	Patient report	Online or by phone	X		
Occupation	Patient report	Online or by phone	X		
Education level	Patient report	Online or by phone	X		
Household Income	Patient report	Online or by phone	X		
Household zip code	Patient report	Online or by phone	X		

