An important secondary outcome assessing efficacy will include the number of medication changes within the 6-month follow-up period. Medication changes will be defined as the addition, removal, or dosage change to any PGx medication or medication within the same drug class. Comparisons of this outcome should estimate differences in trial-and-error drug dosing that is traditionally used in practice. These outcomes are important because if the results suggest that preemptive PGx testing is associated with increased patient treatment satisfaction, a reduction in medication changes, or increased perceived value of PGx testing, these findings would support expanded clinical implementation in medically underserved patients. This might also suggest that PGx could be further used as a tool to minimize disparities in pharmacotherapy. Other secondary outcomes that will be analyzed include: The prescriber acceptance rate of PGx EHR alert recommendations, number of encounters with a healthcare provider over the study period, genotype turnaround time, and estimated time spent discussing medications with a healthcare provider. These outcomes will be used to assess feasibility and will inform design of a large clinical trial to be funded by future grants.

Socioeconomic data collection: We have previously observed significant associations between calculated geographic access scores and rate of PGx drug prescriptions, which considerably strengthened in subanalyses by race. Whether this association is exclusively related to geography and race or whether it is also related to socioeconomic determinants is unknown. Thus, we will test whether socioeconomic status is a social determinant of health related to PGx drug usage. Patients will answer survey questions related to their education, employment, and income (Table 1).

Qualitative data collection: An estimated sample size of 20 patients from the 100 recruited participants will be recruited for this aim. Patient sampling will be aimed at achieving an approximately even distribution of sex (male and female) and race (Latino and black).

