Analysis plan. For Aim 1, implementation outcomes such as prescriber acceptance, turnaround time, and cost will be assessed using descriptive statistics. Differences in patient reported outcomes such as treatment satisfaction, perceived value, and effectiveness outcomes (Table 1) will be initially compared between baseline and 6 months using Student's t-test or Mann-Whitney U test, depending on the data distribution. In addition to univariate analyses, multiple regression models will also be completed for each outcome, adjusted for potential covariates, such as age, race, sex, clinic site, and Charlson Comorbidity Index. In all analyses, a two-sided $P \leq 0.05$ will be considered statistically significant, and all statistical analyses will be completed in R ver. 3.6.3.

For Aim 2, interview transcripts will be managed using data management software (e.g., Nvivo or Atlas.ti). Data will be thematically analyzed using the widely used constant comparative method.¹³ This systematic approach involves several coding steps including identifying concepts and assigning codes, 2) grouping categories of emergent themes, and 3) axial coding to identify thematic properties. To ensure similarities and differences between patients' experiences can be captured, data analysis will be segmented by group and triangulated with survey data collected from healthcare providers (via separate protocol). Triangulation of data between sources also enhances the validity of the findings.¹⁴ Multiple coders, trained in the CCM approach, will conduct the analysis to ensure rigor. Meetings will be held to compare independent coding, discuss differences in interpretation, collapses analyses, and continuously refine the codebooks. Codebooks will be developed with each stakeholder group dataset. Once codebooks are finalized and analyses complete, each analysis will be validated by an additional coder analyzing a subset of the transcripts from each group.¹² Operational and thematic memos will be maintained across data collection and analysis to ensure researcher reflexivity, thematic saturation, and rich description of themes.

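### Aim 1 asks whether PGx testing can be implemented, but its primary feasibility outcome is a change in medication satisfaction, which does not show whether testing was delivered

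*Combined protocol and SAP*

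**What the plan says.** Section 5, Aim 1, sets the question: "Assess the feasibility of preemptive PGx clinical implementation in primary care clinics predominantly serving medically underserved patients". It then says how the question will be answered: "We will assess feasibility of this implementation effort by comparing patient-reported outcomes data abstracted from electronic health records before and 6 months after PGx testing".

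Section 6, Feasibility data collection, names the primary measure: "The primary feasibility outcome will be change in patient treatment satisfaction between baseline and 6 months after PGx testing". The instrument is the TSQM, which "assesses three medication-related domains (effectiveness, side effects, and convenience) to synthesize a global satisfaction score". Table 1 classes treatment satisfaction as an implementation outcome.

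The same section lists further secondary outcomes: prescriber acceptance of PGx alerts, provider encounters, genotype turnaround time and time spent discussing medications. Of these it says: "These outcomes will be used to assess feasibility and will inform design of a large clinical trial". The Analysis plan adds cost and assigns descriptive statistics to acceptance, turnaround and cost. Patient-reported outcomes "will be initially compared between baseline and 6 months using Student's t-test or Mann-Whitney U test, depending on the data distribution", at a two-sided 0.05 level.

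Under Study design, the follow-up questionnaires fall "3 months and 6 months after PGx results are entered into the EHR". Participant Recruitment Methods allows a mailed kit for retesting if genotyping of the initial sample fails.

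**The concern.** The measure called primary for feasibility is an effect measure. It asks whether patients' satisfaction with their medicines changed. It does not ask whether samples gave a reportable result, whether results reached the EHR or whether patients stayed to 6 months. The protocol describes each of these steps, but none appears as an outcome in Table 1 or in the secondary list, and neither does consent.

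The timing rule adds a blind spot. A patient with no result in the EHR has no 3- or 6-month due date, so a plain delivery failure leaves the TSQM comparison without being counted anywhere.

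At stake is the use of the pilot. It is meant to inform a larger trial, whose planning needs these proportions. If the Aim 1 conclusion is drawn from TSQM, it rests on a quantity that can move independently of delivery.

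**Working it through.** **No figure to reproduce.** The sample size of 100 is stated without power, effect size, SD, dropout or a feasibility target.

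**1. Delivery steps against outcomes (sections 5 and 6).**

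| Step | Described in the protocol | Named as an outcome |
|---|---|---|
| Consent | Yes | No |
| Reportable genotype, first sample or retest | Yes | No |
| Result entered in the EHR | Yes; starts the follow-up clock | No; turnaround time only |
| Prescriber response to alert | Yes | Yes, acceptance rate (secondary) |
| 6-month questionnaire completed | Yes; compensated | No |
| Satisfaction with medication | Yes | Yes, primary |

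Acceptance is observed only where an alert fired, and turnaround only where a result came back. Neither counts the patients for whom the process stopped earlier.

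**2. Does the TSQM P value track delivery?** All inputs here are assumptions except n = 100 and the two-sided 0.05 level. A paired test is assumed; the Analysis plan does not state the paired form.

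- *Full delivery, no satisfaction change:* P ≤ 0.05 occurs in 5% of studies, by definition of the test.
- *Poor delivery, 40 of 100 complete, mean change 0.5 SD of the change:* noncentral-t power with 39 degrees of freedom is 0.869.
- *Full delivery, 0.5 SD gain confined to a share f with an actionable result:* the pooled gain is 0.5f SD. With a baseline to 6-month correlation of 0.5, the SD of change is √(2 × (1 − 0.5)) = 1 SD. Power ≈ Φ(0.5f × √100 − 1.96) = Φ(5f − 1.96).

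| f | 5f − 1.96 | Power |
|---|---|---|
| 20% | −0.96 | 17% |
| 30% | −0.46 | 32% |
| 50% | 0.54 | 71% |
| 60% | 1.04 | 85% |

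Delivery is complete in every row of this table, yet the chance of significance runs from 17% to 85%. In the 40-completer case delivery is poor and the chance is 87%. The P value reflects the size and spread of the change and the number of pairs.

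**3. What a proportion would give at n = 100.** The exact (Clopper-Pearson) limits are the 2.5% point of Beta(x, n − x + 1) and the 97.5% point of Beta(x + 1, n − x).

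| x/n | Exact 95% CI |
|---|---|
| 50/100 | 39.8% to 60.2% |
| 80/100 | 70.8% to 87.3% |
| 90/100 | 82.4% to 95.1% |

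The half-width is at most about 10 points, which is enough to plan a larger trial.

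**The case against.** The strongest reply is that the plan does not judge feasibility by TSQM alone. Alert acceptance and turnaround time are expressly used to assess feasibility, cost is described, and the Aim 2 interviews explore barriers and delivery of results. That stands. A reader might infer that process feasibility is ignored, and the documents do not support that. What remains is that these measures are secondary or descriptive and leave out consent, genotyping success and completion.

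A reader might also infer that a non-significant TSQM result would make the programme infeasible. No section says so. The only rule of interpretation, in Feasibility data collection, runs one way: higher satisfaction, fewer medication changes or higher perceived value would each support wider implementation.

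Two further replies narrow the point. The mailed retest means that only patients whose genotyping still fails after any retest lack a follow-up clock, and their number is unknown. The inclusion criteria also select patients thought likely to benefit, so a low actionable share is not an obvious default and no single power figure should be relied on.

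Finally, Table 1 calls satisfaction an implementation outcome, and a pilot may reasonably collect preliminary effect data. That justifies keeping TSQM. It does not make a rating of medication a measure of whether testing was delivered.

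**Conclusion.** The point holds as a mismatch between the Aim 1 question and its primary outcome. It is not an arithmetic error, and no stated figure is wrong. Followed exactly, the plan tests a change in medication satisfaction under a feasibility label and leaves consent, genotyping success and 6-month completion without a defined outcome. Patients who never obtain a result do not appear in the TSQM comparison.

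The conclusion rests on what the TSQM measures and on the list of outcomes, not on the power illustration. The 17% to 85% range depends on an assumed 0.5 SD gain confined to patients with an actionable result, a correlation of 0.5 and 100 complete pairs. It shows only that significance and delivery are separate matters. It would be wrong to read it as the share of sound programmes that the plan would declare infeasible, because the plan has no such rule.

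**What to change.** Amend section 5 (Aim 1) and section 6 (Feasibility data collection and Analysis plan).

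1. Base the Aim 1 feasibility conclusion on three proportions, each with all enrolled patients as the denominator and an exact 95% CI: (a) reportable genotype, on the first sample and after retest; (b) result entered in the EHR; (c) 6-month questionnaire completed. Patients with no result stay in the denominator.
2. Report with these the alert acceptance rate, with alerts fired as its denominator, and the turnaround time already listed.
3. Report consent among patients the coordinator approached, from a simple log. This denominator is not currently planned. It will not cover patients who were only asked by clinic staff or given a flyer and never reached the study team.
4. Do not use the proportion of enrolled patients with at least one alert as a success measure. Alerts depend on a possible interaction with a prescribed drug, so a correctly tested patient with none would count as a failure.
5. Keep TSQM change as the principal patient-reported outcome, reported as an estimate with a 95% CI, and state that feasibility is not inferred from its P value.

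The cost is protocol wording and a coordinator log, with no new patient contact. The small downside is that TSQM is no longer the headline feasibility result.

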Current implementation patterns of PGx testing, as with other innovative technologies, have the potential to increase disparities in health care quality and outcomes, especially if there is greater preexisting need in the populations unable to access them. This phenomenon, known as the Inverse Equity Hypothesis,² will continue to occur unless specific access barriers are overcome when a new technology is implemented.

PGx testing may be particularly beneficial in medically underserved populations by reducing the number of medical encounters required to optimize drug therapy and preserving use of less expensive off-patent drugs – the type drugs most often with PGx guidelines available – for patients predicted to benefit based on their genotype results. This is supported by preliminary data from the University of Florida (UF) Health, which indicate that patients with poor geographic access to healthcare providers are prescribed a higher rate of drugs with PGx guidelines available (PGx drugs). Race compounds this disparity, with underserved black patients having both significantly fewer encounters with healthcare providers and more PGx drug prescriptions than underserved non-black patients. Because medically underserved patients use more PGx medications and visit their provider less often, these patients should benefit the most from preemptive PGx testing, where trial-and-error drug selection could be minimized. Thus, there is a critical need to gather data to inform clinical implementation of PGx testing in medically underserved populations to improve healthcare quality and assure equitable distribution of innovative healthcare technologies.

Most experts agree that clinical PGx implementation will eventually evolve to a preemptive testing model where patients are tested for multiple PGx variants at one time, with these data stored in their electronic health record (EHR) to inform future prescribing.^{3,4} Pre-emptive testing is more efficient than “reactive” testing (i.e. at the time of drug prescribing) because most PGx tests have the most clinical benefit when genotype is known before a medication is administered, reducing the risk of treatment failure or adverse

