2. Understand perspectives on preemptive PGx testing among key stakeholders in the primary care clinics predominantly serving medically underserved patients. We will conduct in-depth, semi-structured interviews with a subsample of recruited patients from Aim 1 and clinicians within the clinic sites to identify influential factors critical to implementing PGx testing, including motivations, barriers, and best practices for the delivery of results.

3. Identify specific socioeconomic characteristics most strongly associated with PGx drug prescription rates. Our preliminary data using EHR data from UF Health show strong correlations between zip code-derived healthcare geographic access scores and rate of PGx drug prescriptions. We aim to use the results of a validated socioeconomic estimation tool as well as individual measures of socioeconomic status in a single predictive model to determine which social determinants most associate with PGx drug prescription rate within the 100 patients from Aim 1.

6. Research Plan:

Study population and setting. This study will include UF Health patients recruited from clinics that serve mostly medically underserved areas. Primarily, this will include the UF Health Family Medicine Eastside and Main St. Clinics, which serve a large number of low-income, black and Latino patients. Overall, we plan to recruit 100 patients from targeted clinics. Inclusion criteria are designed to identify patients who have a high possibility of benefitting from PGx testing.

Inclusion Criteria:

1. Adults (18 years or older) with active prescriptions for at least 3 medications documented within the EHR.
2. At least 1 drug/drug class that could be informed by the PGx test panel (See Appendix A for complete list).
3. A medication change within the past 6 months (associated with a healthcare provider encounter)
4. Self-identify as black or Latino.

Exclusion Criteria:

1. Patients with any history of PGx testing within the EHR.

Participant Recruitment Methods.

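### Medication changes and encounters come only from the EHR, with no rule for care received elsewhere, so lost observation would mostly look like the reduction the plan counts as favourable

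*Combined protocol and SAP*

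**What the plan says.** The protocol's section 6 (Research Plan) describes the population by its link to UF Health at recruitment: "This study will include UF Health patients recruited from clinics that serve mostly medically underserved areas". Two inclusion criteria concern contact with care. The first is "Adults (18 years or older) with active prescriptions for at least 3 medications documented within the EHR". The third is "A medication change within the past 6 months (associated with a healthcare provider encounter", with the bracket closing there. Both describe the present or the past. The sole exclusion is "Patients with any history of PGx testing within the EHR". No criterion concerns where the patient will receive care after enrolment.

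Table 1 lists two effectiveness outcomes, each collected by EHR pull at baseline and 6 months. The row for the first reads "Medication changes EHR data EHR data pull"; the row for provider encounters has the same source. The Study design paragraph confirms that both are abstracted from the EHR. No claims, pharmacy fills, outside records or patient reports are listed for either.

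The Analysis plan compares baseline with 6 months by Student's t-test or Mann-Whitney U, then by regression on covariates. It has no concurrent control, and no rule for missing data or for patients without EHR contact after results. The Feasibility data collection text says of three possible findings, one of them fewer changes: "a reduction in medication changes, or increased perceived value of PGx testing, these findings would support expanded clinical implementation".

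**The concern.** A plain count from the EHR cannot separate a patient whose medicines did not change from one whose changes were made where the record does not see them. Every participant has to be visible in the EHR to be found and enrolled, so the baseline side is favoured. Nothing protects the follow-up side, and its clock starts only when results are entered, so the turnaround time is added time in which to leave.

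Survey retention would not reveal the problem. Questionnaires are completed online or by phone, so a patient who has left UF Health can finish the 6-month survey and appear fully retained while the EHR shows nothing. With no control arm, nothing shares the loss, and adjusting for age, race, sex, clinic site and comorbidity does not restore unseen events.

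At stake is the reading of an outcome the protocol calls important and ties to efficacy. The Background reports "underserved black patients having both significantly fewer encounters with healthcare providers". In such a population a fall in recorded encounters or changes could reflect care received elsewhere, and the planned data could not tell the difference.

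**Working it through.** The documents give no dropout rate, transfer rate, event rate or power calculation, so there is no planned figure to reproduce. The sample size is a recruitment target: "Overall, we plan to recruit 100 patients from targeted clinics". What follows is a set of scenarios.

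**Inputs.** From the documents: n = 100, two-sided 0.05, before-after comparison. Assumed: mean 2 changes and SD 2 in each of two equal periods, within-patient correlation 0.5, no true change, a fraction f leaving UF Health, outside care not visible in the EHR, and a complete baseline. B is the baseline count, Y the recorded follow-up count, D = Y − B.

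**Expected fall.** If leavers go at the start of follow-up, the recorded mean is 2(1 − f): a fall of 10% at f = 0.10 and 20% at f = 0.20. If departures are spread evenly, a leaver is seen for half the period on average and the mean is 2(1 − f/2): falls of 5% and 10%.

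**Chance of P≤0.05, leaving at the start, paired t (normal approximation).** E[Y²] for a visible patient is SD² + mean² = 4 + 4 = 8, so Var(Y) = 8(1 − f) − 4(1 − f)². Cov(Y, B) = 0.5·2·2·(1 − f) = 2(1 − f). Var(D) = Var(Y) + 4 − 2Cov.

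- f = 0.10: Var(Y) = 7.2 − 3.24 = 3.96; Var(D) = 3.96 + 4 − 3.6 = 4.36; SE = √(4.36/100) = 0.209; z = 0.2/0.209 = 0.958; P = Φ(0.958 − 1.96) + Φ(−0.958 − 1.96) = 0.160.
- f = 0.20: Var(Y) = 6.4 − 2.56 = 3.84; Var(D) = 3.84 + 4 − 3.2 = 4.64; SE = 0.215; z = 0.4/0.215 = 1.857; P = 0.459.

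**Even departure.** A leaver is visible for a uniform fraction U of the period, so E[Y²] for a leaver is E[U²]·E[Y(Y − 1)] + E[U]·2 = (1/3)(8 − 2) + (1/2)(2) = 3.

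- f = 0.10: Var(Y) = 0.9·8 + 0.1·3 − 1.9² = 3.89; Var(D) = 3.89 + 4 − 3.8 = 4.09; SE = 0.202; z = 0.1/0.202 = 0.494; P = 0.078.
- f = 0.20: Var(Y) = 0.8·8 + 0.2·3 − 1.8² = 3.76; Var(D) = 3.76 + 4 − 3.6 = 4.16; SE = 0.204; z = 0.2/0.204 = 0.981; P = 0.165.

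**Simulation under the same inputs.** Gamma-Poisson counts with frailty variance 0.5 give variance 2 + 0.5·4 = 4 and correlation 2/4 = 0.5. There were 1,000 runs per cell. Entries are the percentage of trials showing a significant reduction; the nominal rate in that direction is 2.5%.

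| Scenario | Paired t | Two-sample t | Mann-Whitney U |
|---|---|---|---|
| 10% leave at start | 15.6 | 5.6 | 9.8 |
| 20% leave at start | 48.2 | 26.6 | 46.9 |
| 10% leave evenly | 6.4 | 1.7 | 2.6 |
| 20% leave evenly | 16.3 | 4.5 | 7.3 |

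With nobody leaving, the paired t gave 1.5 to 2.2 and the unpaired tests 0.9 or less, because unpaired tests ignore the within-patient correlation and are conservative here. The simulation agrees with the formulas within its sampling error (about 1.6 percentage points when the rate is near 50%).

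**Direction.** A patient who joined UF Health two months before enrolment can meet every criterion and still have four unseen months in a 6-month baseline. With the same inputs, 20% leaving evenly and 20% joining evenly over baseline gave false reductions in 2.7% of trials, close to nominal. The direction therefore depends on leavers outnumbering late joiners.

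**The case against.** A reader might infer that the error always points to a reduction because observation can be lost only after baseline. The documents do not support that. Entry asks for current prescriptions and one change tied to an encounter, which is not stated to be at UF Health. It does not ask for six months of prior UF Health care, and the baseline window itself is not defined. Late joiners bias the other way, and patients with stable split care are under-counted in both periods.

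A reader might also infer that leavers are scored as zero. No such rule is written. It follows only for someone unseen throughout; a patient who leaves part-way is under-counted. That outside care is invisible is likewise an inference, since the documents do not say what reaches the EHR pull.

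On size, holding the SE at 0.20 for 20% leaving at the start would give z = 2 and about 52%. That ignores the variance the unseen patients add; 46% is the consistent figure. Even that needs immediate departure and a paired test, while the Analysis plan names tests without saying they are paired. Fewer encounters, as reported in the Background, is not evidence of transfer of care, and low visit frequency affects both periods.

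Finally, both counts are secondary outcomes in a pilot. The time-with-provider question at 3 and 6 months gives a partial, unplanned check on records with no encounters.

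All of this stands, and it limits direction and size. It does not supply a rule for unobserved time, a second data source or a control arm. Recruitment through UF Health clinics and the EHR still makes the baseline the better-captured period.

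**Conclusion.** The concern holds in a limited form. Followed as written, the plan can turn lost observation into an apparent reduction in medication changes and encounters, and the protocol would count fewer medication changes as support for wider implementation. The likely direction is toward a reduction, without certainty. The primary TSQM outcome is patient-reported and is not affected by this mechanism.

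The size cannot be established from the documents. Under the stated assumptions it ranges from negligible (10% leaving evenly, unpaired test) to serious (20% leaving at the start, with a false reduction in roughly a quarter to a half of trials depending on the test). All of this falls away to the extent that outside care flows into the EHR pull; if it does, the protocol should say so.

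The problem is also distinct from regression to the mean caused by selecting patients with a recent change. That would remain under perfect capture, and this would remain if the third criterion were dropped. It should be corrected before the EHR pull is specified.

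**What to change.** In the existing baseline, 3-month and 6-month surveys, ask whether the patient received care or prescriptions outside UF Health in that period, whether any medicines were started, stopped or changed there, and the date the patient joined or left UF Health care. The dates are essential, because without them observed time cannot be calculated. Both periods must be covered, because adding outside changes to follow-up alone would bias patients with split care toward an increase.

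In the Analysis plan:

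- Define baseline and follow-up windows of equal length.
- State whether outside records reach the EHR pull.
- Treat time outside UF Health care in either window as unobserved, not as time with no events.
- Analyse both counts with days under UF Health care as an offset.
- As sensitivity analyses, (a) add patient-reported outside changes in both periods; (b) restrict to patients with confirmed UF Health care throughout both windows; (c) for survey non-responders, who may include those who left, censor at last EHR contact.

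The cost is a slightly longer survey, some recall error, and some shortened or missing counts. Eligibility, sample size and clinical care need not change. The proportion leaving UF Health care is also useful feasibility data for the larger trial this pilot is meant to inform.
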